To test these hypotheses for each of the secondary objectives 2-5, treatment group comparisons at the end of Phase 1 will be performed using the generalized linear mixed effects model using the link that is appropriate for the endpoint (i.e. logit for binary, cumulative logit for ordered multinomial categories, identity for continuous). These models will account for the clustering within sites and will include gender, presence of atopy and duration of disease as covariates. For continuous data, appropriate transformations will be considered (e.g. log, square root,

rank) to satisfy the assumptions of the analyses. If the remission status for the categorical outcomes is missing, it will be imputed as a treatment failure. Missing data for continuous outcomes will be imputed using multiple imputation techniques. Covariates for imputation will include investigative site, gender, presence of atopy and duration of disease. Each of the secondary outcomes 2-5 will be tested at the two-sided $\alpha=0.01$ to account for multiple testing.

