- 3) Histology Scoring System (HSS): Will include the overall score, grade score, stage score, and the inflammatory and structural sub-scores. Scores will be reported as distal, proximal, and maximum
- 4) HSS score by remission status (complete, partial, and no remission).
- 5) Endoscopy Scoring System (EREFS): Will include the overall score and the inflammatory and fibrostenotic sub-scores. Scores will be reported as distal, proximal, and maximal score.
- 6) EoE Diagnostic Panel (EDP): The summary EoE score (EDP total score) will be a secondary outcome.

Derived Variables.

- 1) HSS scores. Sum of the feature scores divided by the maximum possible score for the biopsy for grade and stage. The total score is the sum of the grade and stage scores. Inflammatory sub-scores include the following features: eosinophils, abscesses, surface layering, and surface necrosis. Structural sub-scores include basal layer hyperplasia, dilated intercellular spaces, apoptotic epithelia, and lamina propria fibrosis.
- 2) HSS remission. HSS remission is defined as a having both a grade and stage total score less than or equal to 3 and an eosinophil grade score no greater than 1. This is calculated separately for distal and proximal biopsies. When both distal and proximal biopsies are in remission, this is considered complete remission, when only one of the two biopsies meet these criteria, it is partial remission. When neither meet these criteria, it is no remission. Analyses will include full remission vs other and full+partial remission vs no remission.
- 3) EREFS. Total EREFS score will be calculated by summing the grades for all five of the features. The inflammatory score contained the sum of the exudate, edema, and furrows scores (this could range from 0 to 5), and the fibrostenotic score contained the sum of the rings and stricture scores (this could range from 0 to 4).
- 4) Adherence. Adherence will be dichotomized into mostly adherent vs not-mostly adherent. The judgement of adherence will be based on questionnaires about food intake and dietitian input. If inconsistent, food diaries will be reviewed. The final adherence call will be provided to the statistician.
- 5) Atopy. Atopy is a multi-faceted disease. Individuals will be defined as atopic if they report a history of asthma, eczema, allergic rhinitis, allergic conjunctivitis, IgE mediating food allergy

and/or atopic dermatitis.

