- 2) To evaluate the effect of each therapy on histological remission defined by a variety of changes in eosinophils, including (a) pre- minus post-therapy peak eosinophil counts; (b) partial

remission (2-14 peak eosinophils/hpf); and (c) complete histological remission (≤ 1 peak eosinophils/hpf).

- 3) To evaluate the effect of each therapy by utilizing the histology scoring system (HSS) created to express the severity and extent of other abnormalities in the gastrointestinal (GI) tract that often accompany eosinophilic inflammation.
- 4) To evaluate endoscopic outcomes as assessed by the endoscopy scoring system (EREFS).
- 5) To determine the impact of each therapeutic intervention on biomarkers using the EoE Diagnostic Panel (EDP).

For secondary objectives 1, the remission rate at the 6-week time point for non-responders in Phase 1 who proceeded to Phase 2 will be summarized separately depending on the treatment patients received during Phase 1. The 95% two-sided confidence interval for the rate will be provided. If the remission rate is missing for patients that entered Phase 2, it will be imputed as a treatment failure.

To test hypotheses for each of the secondary objectives 2-5, treatment group comparisons at the end of Phase 1 will be performed using the generalized linear mixed effects model using the link that is appropriate for the endpoint (i.e. logit for binary, cumulative logit for ordered multinomial categories, identity for continuous). These models will account for the clustering within sites and will consider sex, baseline esophageal eosinophil count, adherence, presence of atopy, and time since diagnosis as covariates. For continuous data, appropriate transformations will be considered (e.g. log, square root, rank) to satisfy the assumptions of the analyses. If the remission status for the categorical outcomes is missing, we will evaluate how to treat the observation. If the study subject prematurely quit the clinical trial, then we will consider the observation a treatment failure. However, if the data was not captured (as in the case of a biopsy which did not capture both distal and proximal findings then we will consider imputation. Missing data for continuous outcomes may be imputed using multiple imputation techniques. Covariates for imputation will include investigative site, sex, presence of atopy and duration of disease. Secondary outcomes 2-5 will be tested at the two-sided $\alpha=0.01$ to account for multiple testing.

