Analyses of Exploratory Endpoint(s)/Outcome(s)

Exploratory Variables:

- 1) Change in Patient Reported Outcome (PRO) metrics (pre- minus post- treatment)
 - a. EoE Adult Symptom Score Activity Index (EESAI)
 - i. VDQ, AMS, Overall PRO
 - b. Adult EoE Quality of Life Score
 - i. Social impact, emotional impact, disease anxiety, eating/diet impact, choking anxiety
 - c. PROMIS General Health Questionnaire
- 2) Clinical parameters
 - a. Baseline disease activity measures (peak eosinophil count, EREFS, HSS)
 - b. Body mass index (BMI)
 - c. Presence of atopy and specific atopic diseases (e.g., is asthma associated with tx response/non-response)
 - d. Demographics (sex, age, race)
- 3) Biomarkers
 - a. Serum food specific IgE

- b. CRD – food specific components for IgE and IgG4
 - c. Serum food specific IgG4
 - d. EDP score
- 4) Skin testing results
- a. Skin prick tests to milk, egg, wheat, soy, peanut, shellfish, fish, and 5 tree nuts.
 - b. Positive is defined as ≥ 3 mm.
- 5) Milk driven T-cells
- a. T-cell count
 - b. Cytokine levels

Exploratory objectives are detailed below:

- 1) To evaluate the clinical and psychosocial effect of each therapy utilizing patient reported outcomes (PROs) to assess EoE symptoms and problems/feelings related to eating.
- 2) To evaluate factors predicting treatment response including
 - a) Clinical parameters
 - b) Serum food specific IgE, CRD, and IgG4
 - c) Skin testing results, in the form of prick and patch testing
 - d) Milk-driven T cells in blood

To test hypotheses for exploratory objective one, we will compare the treatment arms using general linear mixed models as described for the secondary outcome measures. To test hypotheses for exploratory objective 2, we will compare responders to non-responders using the generalized linear mixed effects model using the link that is appropriate for the endpoint (i.e. logit for binary, cumulative logit for ordered multinomial categories, identity for continuous). Covariates will be considered as appropriate. For continuous data, appropriate transformations will be considered (e.g. log, square root, rank) to satisfy the assumptions of the analyses.

Adverse Events

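### The SAP does not pre-specify each continuous outcome's own baseline as a covariate for HSS, EREFS, EDP and the PROs; adding it is cheap, but the gain in precision is unknown and may be negligible

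*SAP*

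**What the plan says.** **Secondary models.** The SAP (Analyses of Secondary Endpoint(s)/Outcome(s)) compares the arms at the end of Phase 1 with generalized linear mixed models, using an identity link for continuous outcomes and two-sided alpha 0.01. The models "will consider sex, baseline esophageal eosinophil count, adherence, presence of atopy, and time since diagnosis as covariates". Protocol 13.4.4 has a shorter list: its models "will include gender, presence of atopy and duration of disease as covariates".

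**Outcomes concerned.** These are the HSS and EREFS scores (by location) and the EDP score: "The summary EoE score (EDP total score) will be a secondary outcome". The SAP does not say whether they are analysed as week-6 values or as change. Protocol 4.4 speaks of change for EDP.

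**PROs.** These are exploratory: "Change in Patient Reported Outcome (PRO) metrics (pre- minus post- treatment". For them, "we will compare the treatment arms using general linear mixed models as described for the secondary outcome measures". Protocol 13.4.5 sets a nominal alpha of 0.05.

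**Imputation.** "Covariates for imputation will include investigative site, sex, presence of atopy and duration of disease". The SAP makes multiple imputation of continuous outcomes optional; Protocol 13.4.4 states it as planned.

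**Availability of baselines.** Protocol 4.4 and 9.1 plan a baseline EDP. Protocol 4.4 places the baseline PROs at screening, while 9.2 and the schedule place them at enrolment. The SAP's exploratory section lists "Baseline disease activity measures (peak eosinophil count, EREFS, HSS" among candidate predictors of response, which implies that baseline HSS and EREFS will exist.

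**The concern.** In a randomized comparison of a continuous score, the score's own baseline is often the most useful covariate. The SAP applies this idea to one outcome family only: it adds baseline eosinophil count, which the protocol list lacks. It does not do so for HSS, EREFS, EDP or the PROs, although it expects to hold their baselines and regards two of them as possible predictors of response.

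What is at stake is power in secondary comparisons at the strict 0.01 level and in the exploratory PRO comparisons. Pre-specification also matters because the trial is open-label (Protocol 4.6): a covariate chosen after the data are seen is open to challenge.

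**Working it through.** **Inputs from the documents.** The plan states no power for these outcomes, so there is no figure to reproduce. The 60 per arm comes from Protocol 13.6 (45% against 70%, at least 80% power, two-sided 0.05). It checks out: power at 60 per arm is 79.9% by the pooled normal formula and 80.6% by exact enumeration of the likelihood ratio test. Enrolment is 68 per arm.

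**Assumed inputs.** A true difference of 0.5 SD, and three within-arm correlations: a (baseline eosinophil count with outcome), b (eosinophil count with own baseline) and r (own baseline with outcome).

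**HSS, EREFS and EDP taken as week-6 values, alpha 0.01.**
- Variance explained by eosinophil count alone: a².
- With own baseline added: (a² + r² − 2arb)/(1 − b²).
- Power = Φ(0.5/√[(2/60)(1 − R²)] − 2.576).

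Worked case, a = 0.25, b = 0.4:
- Eosinophil count only: R² = 0.0625, SE = √(0.0333 × 0.9375) = 0.177, power 60%.
- Own baseline added, r = 0.5: R² = (0.0625 + 0.25 − 0.10)/0.84 = 0.253, SE = 0.158, power 72%.
- r = 0.3: R² = 0.0925/0.84 = 0.110, power 63%.
- r = 0.2: R² = 0.0625/0.84 = 0.074, power 61%.

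Range over a = 0.2-0.35 and b = 0.3-0.7. The upper values of b allow for HSS itself scoring eosinophils ("Inflammatory sub-scores include the following features: eosinophils, abscesses, surface layering, and surface necrosis"). Only combinations are kept in which the eosinophil coefficient, (a − rb)/(1 − b²), is not negative; a negative one would mean that, given own baseline, a higher baseline count predicts a better score.

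| r | Power gain (points) | Residual variance cut |
|---|---|---|
| 0.2 | 0-1 | 0-2% |
| 0.3 | 0-4 | 1-7% |
| 0.5 | 9-14 | 15-22% |

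**PRO change scores, alpha 0.05, eosinophil count taken as uninformative.** Let k = baseline SD / week-6 SD. The change score has variance 1 + k² − 2rk; with own baseline in the model the variance is 1 − r².
- k = 1: the cut is (1 − r)/2, that is 35% at r = 0.3 (power 64% to 82%) and 20% at r = 0.6 (86% to 93%).
- k = 0.5: the cut is 4% at r = 0.3, 0% at r = 0.5 and 2% at r = 0.6.

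**Missing baselines.** If a fraction m lack the baseline and are kept by mean fill with an indicator, R² ≈ a² + (1 − m)(R² with own baseline − a²). At r = 0.5, with a = 0.2-0.3 and b = 0.3-0.5, power is 72-74% with none missing, 68-70% at m = 0.3 and 65-67% at m = 0.5.

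**Imputation.** The SAP list names neither own baseline, nor eosinophil count, nor treatment arm. Take 68 per arm with 8 missing. Outcomes imputed without arm carry no treatment difference, so the expected effect shrinks to 0.5 × 60/68 = 0.44 SD. In simulation at r = 0.5 (a = 0.25, b = 0.4, own baseline in both models), power is about 55% without arm in the imputation model. It is close to 70% with arm included, and also close to 70% for complete cases.

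**The case against.** The strongest reply is that this is a preference, not an error. The SAP only undertakes to consider its covariates, so own baseline can still be added. That stands: the point is absent pre-specification, not a prohibition.

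A second reply is that r may well be low. Entry requires at least 15 eosinophils/hpf, which may narrow the baseline range, and 45% to 70% of patients are assumed to remit by week 6. This is inference, but it points away from r = 0.5, the only value tried that gives a material gain for HSS, EREFS and EDP. It stands as a reason to expect little.

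Third, PRO change scores already use the baseline. This holds in part. Subtraction fixes the coefficient at 1; estimating it is at least as precise in large samples, though nearly equal when the baseline SD is half the week-6 SD.

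Fourth, imputation is optional in the SAP, and arm may simply have been taken for granted in the list. Both are fair. The imputation remark is therefore conditional on imputation being used.

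A reader might infer that the comparisons are biased or the type I error inflated. The documents do not support that: under randomization, leaving out a baseline covariate costs precision only when outcomes are fully observed. If missingness depends on own baseline, its absence does weaken the missing-at-random assumption. A reader might also credit own baseline with its full r² (25% of variance at r = 0.5), but that ignores what the listed eosinophil count already explains.

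**Conclusion.** The omission is real in both documents, for the continuous HSS, EREFS, EDP and PRO comparisons. It contradicts no stated figure and leaves the primary analysis untouched. For HSS, EREFS and EDP as week-6 values, the gain forgone runs from nothing at r = 0.2 to 9-14 power points at r = 0.5. For PRO change scores it runs from near zero to a 35% variance cut in the cases tried. All of this rests on assumed correlations, SD ratios and a 0.5 SD effect, and nothing in the documents shows where r lies. If HSS, EREFS or EDP is analysed as change, the change-score formula applies instead. The point is an optional, cheap improvement and should not be presented as a flaw that endangers the secondary results.

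**What to change.** In the SAP's secondary section, and by reference in its exploratory section:

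1. For each continuous HSS, EREFS, EDP and PRO outcome, pre-specify its own baseline as a covariate: the same score and, for HSS and EREFS, the same location. Do this whether the outcome is the week-6 value or the change. On the same scale the two forms then give the same treatment comparison, apart from sign.
2. If multiple imputation is used, put every analysis-model term into the imputation model, including treatment arm, baseline eosinophil count and own baseline.
3. State a rule that keeps patients with a missing baseline, for example mean fill with a missing indicator. EDP, EREFS and location-specific HSS baselines may all be missing where an earlier or outside EGD served as baseline (Protocol 9.1) or a biopsy lacked a segment.
4. Name the visit that supplies the PRO baseline; Protocol 4.4 and 9.2 differ.

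The rest of the covariate list can stay. Whether adherence, which is judged during the diet, belongs in these models is a separate question.

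Cost: wording only and no new data collection; one or two extra terms per model; and a smaller gain where baselines are missing, in numbers the documents do not give.

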The instructions for the 1FED and 6FED therapeutic diets will be standardized across sites by providing consensus documents produced by registered dietitians who are experts in dietary elimination in EoE. There are currently no validated dietary questionnaires for measuring food allergen intake in adults in the US. Dietary intake and *consumption* of the allergens will be measured at the start of the trial and adherence to the dietary elimination (i.e. *avoidance* of the allergens) during the trial will be measured using modified versions of the NCI's usual dietary intake/diet history questionnaires and 3-day food diaries (<http://cancercontrol.cancer.gov>). Stool samples may be collected from subjects who consent to stool collection to evaluate the effect of diet on the microbiome.

Similarly, standardized instructions for using SGC will be provided, based on our prior studies. We have chosen to use fluticasone propionate (FP) rather than budesonide in this study, given our prior work in this area, and our recent finding that high-dose fluticasone is well tolerated and highly effective, and our preliminary findings concerning esophageal transcripts that predict responsiveness to FP therapy. The study design is shown schematically in Figure 1 Study Design Flowchart.

Figure 1 Study Design Flowchart

Analysis Populations

The analysis population for the primary and secondary endpoints will be the intent-to-treat population with the goal of including patients who have been randomized in the analyses. However, we will exclude patients who were inappropriately randomized and never completed the enrollment visit. Patients for which the primary endpoint of histological remission cannot be determined will be imputed as treatment failures. To maximize comparability with other studies, we will also perform per protocol analyses, including only individuals who complete the study phase of interest for all proposed studies.

Variables of Interest

Primary outcome:

- 1) Remission rate (<15 peak eosinophils/hpf)

Secondary outcomes:

- 1) Change in eosinophils/hpf from baseline to post treatment
- 2) Remission status: Patients will be classified into 3 remission categories: complete histological remission (≤ 1 peak eosinophils/hpf); partial remission (2-14 peak eosinophils/hpf); no remission (≥ 15 peak eosinophils/hpf)

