- 6) Time since diagnosis will be calculated as the study date at baseline minus the date at diagnosis.

Prior to any hypothesis testing, all variables will be reviewed for plausibility. Any values which are considered suspect will be reviewed by the clinical team to ensure accuracy. Continuous data will be evaluated for distributional assumptions of normality. Natural log-transformation will be considered for right skewed non-normally distributed data (the most typical skew seen in physiologic data).

Demographics/Patients Characteristics

Demographic, patient characteristics, medication use and study completion status will be summarized for the two treatment groups using median [interquartile range] for continuous variables and frequency and percentages for categorical variables. Treatment comparisons will be performed for demographics and patient characteristics using the Wilcoxon Rank sum test for continuous variables and the Fisher's Exact test for categorical variables. All tests will be conducted at $\alpha=0.05$.

Demographics and patient characteristics will be summarized within each Phase 1 treatment group between patients who choose to continue into Phase 2 and those who opt out. Any apparent difference will be noted.

Analysis of Primary Outcome

Primary Objective:

1. Determine the rate of remission following 1FED vs. 6FED and evaluate the relative efficacy of these dietary therapies.

Statistical hypothesis for the primary outcome:

H0: $p_{1FED} = p_{6FED}$

H1: $p_{1FED} \neq p_{6FED}$

where p_{1FED} =percentage of patients in histologic remission (<15 peak eosinophils/hpf) on the 1FED diet at end of Phase 1

p_{6FED} =percentage of patients in histologic remission (<15 peak eosinophils/hpf) on the 6FED diet at end of Phase 1

This hypothesis will be tested using the generalized linear mixed effects model with the logit link (for binary outcome) that accounts for the clustering within sites. Covariates to be considered in this model are sex, current age, baseline esophageal eosinophil count, adherence, presence of atopy, and time since diagnosis. All tests will be conducted at $\alpha=0.05$.

Analyses of Secondary Endpoint(s)/Outcome(s)

Following are the secondary objectives of the study:

- 1) To extend Phase 1 of this study with a prospective non-blinded trial that determines the rate of remission following SGC in the 6FED non-responders and the rate of remission following 6FED in the 1FED non-responders (Phase 2).

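### The imputation list for continuous secondary outcomes does not name treatment arm or the outcome's baseline; used as written, it would shrink imputation-based diet differences by about the fraction missing.

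*SAP*

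**What the plan says.** The SAP, under Analyses of Secondary Endpoint(s)/Outcome(s), states "Missing data for continuous outcomes may be imputed using multiple imputation techniques" and then "Covariates for imputation will include investigative site, sex, presence of atopy and duration of disease". Protocol 13.4.4 has the parallel pair: "Missing data for continuous outcomes will be imputed using multiple imputation techniques" and "Covariates for imputation will include investigative site, gender, presence of atopy and duration of disease". Imputation is therefore planned in the Protocol and optional in the SAP, and the four variables are the same.

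The imputed data feed 1FED versus 6FED comparisons at the end of Phase 1, tested at two-sided alpha 0.01. The continuous outcomes concerned include change in peak eosinophil count, HSS, EREFS and the EDP score. Protocol 13.4.5 extends the same imputation rule to the symptom and eating outcomes.

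In the Protocol, the imputation list matches the secondary analysis model, which has site, gender, atopy and duration of disease. In the SAP the two no longer match: the analysis models "will consider sex, baseline esophageal eosinophil count, adherence, presence of atopy, and time since diagnosis as covariates", while the imputation list is unchanged.

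**The concern.** An imputation model should contain at least the variables whose effect the analysis will estimate. Here that effect is the difference between diets. If arm is left out, missing values in both arms are drawn from one pooled distribution, and the imputed patients dilute the contrast. None of the four named variables can stand in for arm. Protocol 13.3 randomizes 1:1 within site, so site says nothing about diet, and randomization balances the patient characteristics in expectation.

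The diluted results would make 1FED look closer to 6FED on histology, endoscopic score and EDP score than it is. That is an awkward direction of error for a trial that asks whether a less restrictive diet is good enough.

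Leaving out the outcome's baseline is a lesser gap. It matters when missingness depends on that baseline.

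**Working it through.** **Figures in the plan.** The documents give no number for the imputation. Their only related figure is the drop-out allowance in Protocol 13.6, which belongs to the primary endpoint: 60 per arm for at least 80% power (45% versus 70%, two-sided 0.05, likelihood ratio test), raised to 68. The power reproduces: exact enumeration gives 80.6%. The allowance is stated as about 15%, but (68 − 60)/68 = 11.8%. Neither is a missing rate for the secondary outcomes, so every fraction below is an assumption.

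**Closed form.** Let D be the true arm difference, f1 and f6 the fractions missing on 1FED and 6FED, and w the 1FED share of observed patients, w = (1 − f1)/[(1 − f1) + (1 − f6)]. With arm absent, imputed values centre on the pooled observed mean. That mean lies (1 − w)D from the 1FED mean and wD from the 6FED mean, so

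expected difference = D × [1 − f1(1 − w) − f6·w].

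- Equal fractions f: w = 0.5 and the factor is 1 − f. At 5% missing it is 0.95, and at 11.8% it is 0.882.
- 5% on 1FED and 15% on 6FED: w = 0.95/1.80 = 0.528, and the factor is 1 − 0.05 × 0.472 − 0.15 × 0.528 = 0.897.

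**Simulation.** Assumptions: D = 0.50 SD, 68 per arm, 10 sites, 20 imputations, Rubin's rules, baseline-outcome correlation 0.4, values missing completely at random, 3,000 trials per row. The analysis model has arm, sex, atopy and duration. The Monte Carlo standard error is at most 0.0035.

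| Missing | Closed form | List as written | List plus arm | Complete cases |
|---|---|---|---|---|
| 2% | 0.490 | 0.490 | 0.501 | 0.501 |
| 5% | 0.475 | 0.472 | 0.498 | 0.498 |
| 10% | 0.450 | 0.450 | 0.503 | 0.503 |
| 11.8% | 0.441 | 0.442 | 0.503 | 0.503 |
| 15% | 0.425 | 0.422 | 0.498 | 0.498 |
| 20% | 0.400 | 0.404 | 0.508 | 0.508 |
| 5% / 15% by arm | 0.449 | 0.448 | 0.501 | not tabulated |

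A second simulation (1,500 runs) balanced the arms within site and put site and baseline in the analysis model. At 5%, 11.8%, 15% and 25% missing, the list as written gave 0.478, 0.436, 0.412 and 0.358. The list plus arm gave 0.506, 0.501, 0.494 and 0.494. The ratios give shrinkage of 5.5%, 13.0%, 16.6% and 27.5%.

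The small excess over the closed form comes from site. With 10 sites there are 6.8 patients per arm per site. Of the other patients at a missing patient's site, only (6.8 − 1)/(13.6 − 1) = 46% share that patient's arm. The imputed values therefore lean slightly towards the opposite diet, by (0.54 − 0.46) = 0.08 of D, which adds about 0.08 × 15% = 1.2 points at 15% missing.

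**Error rates at alpha 0.01.** With no true difference, the list as written rejects in 0.8%, 0.3% and 0.3% of trials at 5%, 11.8% and 15% missing (first simulation), so the test is conservative. In the second simulation, at 15% missing and D = 0.50 SD, power is about 33% for the list as written, 52% with arm added and 57% for complete cases.

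**The case against.** The strongest reply is that the text does not say arm is left out. To say that a list will include certain covariates does not limit it to them. The analysis-model lists do not name arm either. The SAP's primary model reads "Covariates to be considered in this model are sex, current age, baseline esophageal eosinophil count, adherence, presence of atopy, and time since diagnosis", and that model exists to compare the diets. In these documents, covariates may simply mean variables other than treatment. This stands, and it is why the point is conditional. It does not settle the matter, because the analysis sentences are tied to a treatment comparison and so imply arm, whereas the imputation sentence has no such tie.

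The second reply is that the harm needs three things together: imputation is used, the list is taken as complete, and outcomes are missing. That also stands. The SAP makes imputation optional, and Protocol 9.4 collects biopsies and questionnaires at early withdrawal, so drop-out overstates missing outcomes. At 2% to 5% missing, the simulated shift is about 0.01 to 0.03 SD.

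A reader might infer more than the documents support:

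- **That continuous outcomes will often be missing.** The SAP's mention of "a biopsy which did not capture both distal and proximal findings" belongs to its rule for categorical remission status. Peak count is taken over the whole esophagus (Protocol, Introduction), so it need not be missing when one level is.
- **That the rule governs the imputation sensitivity analysis of the primary endpoint (Protocol 13.4.3).** That section names no imputation variables, and the list follows the rule for continuous outcomes in a later section. The link is speculation.
- **That false positives are at risk.** The bias is towards no difference.
- **That adding arm makes imputation better than complete cases.** With data missing completely at random it does not.

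Whether imputation is mandatory (Protocol) or optional (SAP) is a separate discrepancy.

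**Conclusion.** The point holds in a limited form. Both documents give an explicit imputation list without treatment arm or the outcome's baseline, and nothing elsewhere supplies them. Followed as written, the rule does worse than not imputing: at an assumed 11.8% missing, a true 0.50 SD difference is estimated as 0.44, against 0.50 from complete cases. The proportional shrinkage is close to the fraction missing, whatever the effect size. It reaches about 15% or more only if about that share of outcomes is missing, which the documents do not suggest for these outcomes.

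The effect is confined to imputation-based secondary comparisons and, through Protocol 13.4.5, the patient-reported outcomes. The primary analysis is unaffected because missing remission is set to failure. The SAP also states that "we will also perform per protocol analyses, including only individuals who complete the study phase of interest", and those analyses of completers are unaffected too.

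The sizes rest on values missing completely at random within arm. The 68 per arm, 10 sites and 0.4 correlation are illustrative.

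**What to change.** Replace the SAP sentence on imputation covariates with:

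> The imputation model will include randomized treatment arm, investigative site, sex, presence of atopy, time since diagnosis, baseline esophageal eosinophil count and, where available, the baseline value of the outcome.

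State that the same model applies to patient-reported outcomes if they are imputed. Adherence is left out of the sentence because the SAP only considers it for the analysis model; whether it belongs there is a separate question.

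The cost is one SAP sentence and no new data collection. Some baselines may be absent, for example EDP or EREFS where an outside endoscopy served as baseline (Protocol 9.1). They can be imputed in the same model. If the sponsor already intends to include arm, the sentence only records it.

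### Does the secondary level of 0.01 fail because the SAP does not say which measures it covers?

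*SAP*

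**What the plan says.** The SAP section on secondary endpoints numbers five objectives. Objective 1 (Phase 2 remission rates) is estimated with a 95% confidence interval and not tested. For the rest, the SAP says: "To test hypotheses for each of the secondary objectives 2-5, treatment group comparisons at the end of Phase 1 will be performed". The same paragraph closes with the level: "Secondary outcomes 2-5 will be tested at the two-sided $\alpha=0.01$ to account for multiple testing". Protocol 13.4.4 sets the same level for each of items 2-5, and there only the objectives carry numbers.

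Objective 2 concerns "histological remission defined by a variety of changes in eosinophils, including (a) pre- minus post-therapy peak eosinophil counts", then partial and complete remission.

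The SAP section Variables of Interest adds a second numbered list, outcomes 1 to 6:

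- Outcome 1: "Change in eosinophils/hpf from baseline to post treatment".
- Outcome 2: remission in three ordered categories (complete, partial, none).
- Outcome 3, HSS: "Will include the overall score, grade score, stage score, and the inflammatory and structural sub-scores. Scores will be reported as distal, proximal, and maximum".
- Outcome 4: HSS broken down by remission category.
- Outcome 5, EREFS: "Will include the overall score and the inflammatory and fibrostenotic sub-scores. Scores will be reported as distal, proximal, and maximal score".
- Outcome 6, the EoE Diagnostic Panel (EDP): "The summary EoE score (EDP total score) will be a secondary outcome".

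Under Derived Variables, the SAP also plans two dichotomies of HSS remission.

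**The concern.** An adjusted level means something only if the set of tests it covers is known. Here the level is stated and the set is not. Neither document gives a familywise target or a divisor. HSS comes as five scores at three locations and EREFS as three scores at three locations, with none marked as the lead.

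The label adds doubt. Read against the outcome list, 2-5 leaves out eosinophil change (1) and EDP (6), and takes in HSS by remission category (4), which as worded is not a comparison of diets.

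At stake is the standing of the secondary results. If many correlated scores are tested at 0.01 and the favourable ones are put forward as adjusted for multiplicity, the error rate behind that claim is higher than the level suggests. The sponsor, investigators and study staff know the assignments (Protocol 4.6), so leaving the choice of score or location open is less comfortable than it would be in a masked trial.

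**Working it through.** **Where 0.01 could come from.** Assume a familywise target of 5%. The SAP states 0.05 for the primary test only, so its use here is an assumption. Bonferroni then gives 0.05/4 = 0.0125, 0.05/5 = 0.01 and 0.05/6 = 0.0083. Five tests reproduce the plan's figure exactly. The documents do not say that this was the derivation.

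**Counting the measures.** Eosinophil change 1, remission status 1, HSS 5 × 3 = 15, EREFS 3 × 3 = 9, EDP total 1. The sum is 1 + 1 + 15 + 9 + 1 = 27, or 29 with the two HSS-remission dichotomies. At a single location it is 1 + 1 + 5 + 3 + 1 = 11. With total scores only, at three locations, it is 1 + 1 + 3 + 3 + 1 = 9.

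**Error rate by reading.** For k tests at 0.01, the bound under any correlation is k × 0.01, and the independent value is 1 − 0.99^k. The last column is the simulated chance of at least one p < 0.01 when the diets differ on nothing tested. The simulation used 60 per arm, t-tests in place of the mixed model, 20,000 trials per setting and a Monte Carlo standard error of at most 0.26 points. Scores were built from features at two locations, and the mean correlation over the 27 measures was set between 0.28 and 0.82. The documents give no correlations, so these are assumptions.

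| Reading | k | Bound | Independent | Simulated |
|---|---|---|---|---|
| One test for each of objectives 2-5 | 4 | 4% | 3.9% | 3.1% to 4.0% |
| Both objective 2 outcomes kept | 5 | 5% | 4.9% | 3.6% to 4.6% |
| Objective 2 parts (a), (b), (c) tested separately | 6 | 6% | 5.9% | not run |
| Total scores, three locations | 9 | 9% | 8.6% | 4.2% to 7.6% |
| All scores, one location | 11 | 11% | 10.5% | 4.2% to 7.7% |
| All listed measures | 27 | 27% | 23.8% | 5.4% to 14.6% |
| Plus HSS-remission dichotomies | 29 | 29% | 25.3% | 6.3% to 15.3% |

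A simpler check on 27 correlated normal statistics gave 19.3% at a common correlation of 0.3, 14.4% at 0.5 and 4.4% at 0.9. With 0.7 within and 0.3 between objectives it gave 13.1%. Independence is only a ceiling: the HSS total is grade plus stage, and the sub-scores regroup the same features.

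**Which reading the text supports.**

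- The opening of the SAP paragraph names objectives 2-5, and its close says outcomes 2-5. The protocol has nearly the same closing sentence and no numbered outcome list. The outcome-list reading would leave EDP without a level although objective 5 is expressly to be tested, and would bring in an analysis that does not compare diets. The word is a carry-over from the protocol; objectives are meant.
- Objective 5 has one named variable, the EDP total.
- Objective 2 has two listed outcomes, not three. Partial and complete remission form one three-category variable, and the SAP provides a cumulative logit model for ordered categories.
- For HSS and EREFS the SAP says location scores are reported. It does not say each is tested at 0.01.

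Two outcomes for objective 2, one HSS score, one EREFS score and the EDP total make five tests, and 5 × 0.01 = 0.05.

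**The case for a change.** The best case for a change is that prespecification costs little and does real work here. The trial is open-label. The SAP itself foresees biopsies that miss the distal or proximal segment, so the choice of location could follow data availability. The all-null calculation is also not the only relevant one. The trial is designed around 45% against 70% remission, so the diets may well differ on eosinophils. If they differ there and not on EREFS, the chance that at least one of the nine EREFS measures gives p < 0.01 is 2.8% to 5.9% under the same assumed correlations, against 1% for a single named score.

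Part of this stands. For objective 2 the plan does not say whether one or two tests are meant, and for objectives 3 and 4 it does not mark the lead score and location. The rest is weaker. All scores and locations are to be reported, so selective emphasis would be visible. The overall score is listed first for both instruments and is the ordinary choice of lead. The maximum parallels the way Protocol section 1 defines the peak count, over the whole esophagus. Per-protocol repeats are given a subsidiary purpose, comparability with other studies. The larger error rates need a familywise target, a set of correlations and a decision to test every location, none of which the documents state.

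**Conclusion.** No change is needed. On the plainest reading 0.01 is adequate: at most 4% with one test per objective and at most 5% with both objective 2 outcomes, whatever the correlation. With 9 to 11 tests the simulated rate is 4.2% to 7.7%, so any excess over an assumed 5% target is under three points. Only testing all 27 measures as adjusted claims takes it materially higher: 5.4% to 14.6% in the structured simulation and up to 19.3% in the simpler check at a common correlation of 0.3. The SAP does not set that plan out.

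The label is a clerical slip that its own paragraph and Protocol 13.4.4 resolve. The unnamed HSS and EREFS lead is missing detail that analysts can fill sensibly, by leading with a total score and treating sub-scores and other locations as supportive. No error rate stated in the documents is missed, and the primary comparison at 0.05 is not affected. This rests on the 5% target and the correlations being assumptions, and on taking the SAP's word that location scores are for reporting.
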